**Study Principal Investigator:**

[name]

Department of Pediatrics

[name]

[name]

[contact]

email: [contact]

Study Title	Encouraging Healthy and Sustainable Dietary Substitutions
Funder	National Heart, Lung, and Blood Institute
Clinical Phase	NA
Study Rationale	
 
The foods people eat have major implications for both human health and environmental sustainability. Approximately 20% deaths in the US are attributed to unhealthy diet and more than 30% of all anthropogenic greenhouse gas emissions are caused by food production.
 
Recently, researchers have identified four simple dietary substitutions that are healthier (i.e., they would improve diet quality and thus reduce risk of diet-related disease) and more environmentally sustainable (i.e., they would reduce carbon emissions associated with food production): replacing beef or pork entrees with chicken or vegetarian entrees; replacing juice with whole fruit; replacing dairy milk with non-dairy alternatives like soy or almond milk; and replacing sugar-sweetened beverages with water.
 
However, it remains unknown how to encourage people to adopt these healthy and sustainable dietary substitutions. Messages about health, the environment, or both health and the environment could encourage these substitutions, but limited research has tested these messages against one another.
 
Emerging adults merit special attention in research on healthy and sustainable dietary substitutions because they have worse dietary quality than older adults and because their dietary behaviors track into later adulthood.
 

Study Objective(s)	
Primary
 
 
To evaluate whether health, environment, or health + environment messages elicit higher perceived message effectiveness than control messages.
 
 
Secondary
 
 
To evaluate whether health, environment, or health + environment messages elicit higher perceived message effectiveness than one another.
 

Study Design	Randomized experiment.
Subject Population	
Inclusion Criteria
 
 
1. Age 18-25
 

key criteria for Inclusion and Exclusion:	
2. Reside in the United States  3. Able to complete a survey in English
 
Exclusion Criteria
 
 
1. Under the age of 18 or over the age of 26
 
2. Reside outside of the United States
 
3. Unable to complete a survey in English
 

Number of Subjects	1,600
Study Duration	Each subject's participation will last approximately 10 minutes. The enrollment period is expected to last ~1-2 weeks.
Study Phases	
There are two phases:
 
 
(1) Screening: screening for eligibility and obtaining consent and
 
(2) Intervention: study intervention/experimental treatment.
 

Efficacy Evaluations	The primary outcome is perceived message effectiveness for encouraging healthy and sustainable dietary substitutions. It will be measured with 4 items adapted from prior studies.
Statistical and Analytic Plan	
Primary outcome
 
 
• We will use linear mixed models to examine the effect of each intervention topic (health, environment, or health + environment) on perceived message effectiveness compared to the control.
 
 
Secondary outcomes
 
 
• We will use linear mixed models to examine the effect of each intervention topic on perceived message effectiveness compared to the other intervention topics.
 

Data and Safety Monitoring Plan	
 
• The principal investigator is responsible for data quality management and ongoing assessment of safety.
 

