## Exclusions

Participants will be excluded if they are younger than 18 years old or older than 25 years old, do not complete the survey, or complete the survey implausibly quickly, defined as completing in <1/3 median survey completion time in a soft launch of the survey.

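### Does the synopsis age exclusion, set at 26 rather than 25, let ineligible participants into the trial?

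*Combined protocol and SAP*

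**What the plan says.** Eligibility by age is stated three times in the combined protocol and SAP.

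- **Synopsis, Inclusion Criteria:** ages 18 to 25.
- **Synopsis, Exclusion Criteria:** "Under the age of 18 or over the age of 26".
- **Exclusions section of the analysis plan:** "Participants will be excluded if they are younger than 18 years old or older than 25 years old". The same sentence also removes people who do not finish the survey or who finish it implausibly quickly.

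The other two synopsis exclusions are "Reside outside of the United States" and "Unable to complete a survey in English". Each is the exact opposite of its inclusion criterion. The synopsis also describes a first phase of "screening for eligibility and obtaining consent", placed ahead of the intervention phase.

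**The concern.** Each synopsis exclusion appears meant to restate an inclusion criterion in the negative. Residence and English do so, and so does the lower age bound. The upper age bound does not: 26 is the one age that the inclusion list leaves out and the exclusion list fails to catch. It also disagrees with the Exclusions section by one year.

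An eligibility mismatch deserves a check because it can have practical effects. If sites or survey programmers work from different lines, the enrolled population may differ from the analysed one. Here the General Principles section says that all randomized participants will be analysed, while the Exclusions section removes anyone over 25. A randomized 26-year-old would fall between those two statements. The question is whether the plan, followed as written, could produce such a person.

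**Working it through.** The documents give no figure to reproduce on this point. The check is to apply each rule to age in completed years and see who is left.

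**Inputs**

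| Rule | Source | Ages left | Count |
|---|---|---|---|
| A: meets inclusion | Synopsis, Inclusion Criteria | 18 to 25 | 25 − 18 + 1 = 8 |
| B: not caught by synopsis exclusion | Synopsis, Exclusion Criteria | 18 to 26 | 26 − 18 + 1 = 9 |
| C: not caught by analysis-plan exclusion | Exclusions section | 18 to 25 | 25 − 18 + 1 = 8 |

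**Combining them**

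- Synopsis alone (A and B): 18 to 25, 8 ages.
- All three (A, B and C): 18 to 25, 8 ages.
- B and C without A: 18 to 25, 8 ages.
- Ages outside A but not caught by B: 26 only.

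The only age on which the rules differ is 26. It fails A, so such a person is ineligible at screening, and it fails C, so such a person would be removed from the analysis in any case. Replacing 26 by 25 in rule B gives the same set, 18 to 25, in every combination that includes A or C.

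**Does another reading of the wording matter?** One could take the synopsis exclusion to mean past the 26th birthday, which would make it agree with an inclusion range of 18 to 25 completed years. Applied consistently, that reading turns the Exclusions section into past the 25th birthday, which would remove most 25-year-olds whom the inclusion criterion admits. The two exclusion statements therefore differ by one year on any single reading. Completed years is the reading under which two of the three statements agree, and the synopsis exclusion is then the odd one out.

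**Effect on size and power.** With the criteria applied jointly, the change in enrolled or analysed number is 0, so the planned 1,600 (400 per arm) and its power stand. For reference, take a two-arm contrast with N = 800, f = 0.10, m = 2 ratings, correlation 0.5 and alpha 0.05. The noncentrality is f² × N × m / (1 + (m − 1) × 0.5) = 0.01 × 800 × 2 / 1.5 = 10.67, which gives power 0.904, in line with the stated 90%. The age wording enters none of these inputs.

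**The case for a change.** The strongest case for acting is practical. The study is an online survey, and the documents do not give the screener's age question or cut-off. If the screener had been programmed from the synopsis exclusion line alone, 26-year-olds could be randomized and then dropped under the Exclusions section, despite the statement that all randomized participants are analysed. The correction costs one digit, and a pre-specified document ought to state eligibility the same way throughout.

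The mismatch stands, and so does the point that zero effect depends on the criteria being applied jointly. Two things limit the rest.

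First, the misprogramming is hypothetical. The inclusion criterion comes first in the synopsis, and screening precedes the intervention.

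Second, even then the damage would be limited. Age is fixed before randomization, so removing people by age cannot bias the comparison between arms; it can only cost numbers. As an illustration, assume that enrolment were spread evenly over the 9 ages from 18 to 26 and that nobody was replaced. About 1,600 / 9 = 178 people would be dropped, leaving 1,422, or about 356 per arm. For a two-arm contrast with N = 711 the noncentrality is 0.01 × 711 × 2 / 1.5 = 9.48, and power is about 0.87 instead of 0.90. The even spread is my assumption. With no 26-year-olds enrolled the loss is nil, so the range under this scenario runs from 0 to about 178 people.

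There is also less of a contradiction here than appears. An exclusion list does not admit anyone; it only removes people from among those who meet the inclusion criteria. A bound that is one year too loose is redundant and does not conflict with the inclusion rule.

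**Conclusion.** The discrepancy is real but clerical, and no change to the plan is needed. Followed as written, the plan enrols and analyses ages 18 to 25 only, the same 8 years of age as if the synopsis exclusion read 25. Expected change in enrolled or analysed number is 0, and the estimand, the power and the interpretation are untouched.

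This rests on two assumptions: that age is taken in completed years, and that screening applies the inclusion criterion together with the exclusions, which is ordinary practice. The documents contain nothing against either. Whoever next edits the synopsis may tidy the digit, but doing so would alter nothing that the trial does or can conclude.

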## **Introduction**

The goal of the analyses described here is to use data we collected through an online randomized experiment to examine consumer responses to different messages about healthy and sustainable dietary substitutions. This analysis examines the effect of different message topics (control vs. health vs. environment vs. health + environment) on perceived message effectiveness for encouraging the healthy and sustainable dietary substitutions. This analysis plan pre-specifies the analyses before collecting data and therefore serves as our ex-ante planned analysis.

## **Study Protocol**

Participants will complete an online survey programmed in Qualtrics. After providing informed consent, participants will complete 4 experiments in random order: 1 for each of 4 target dietary substitutions (beef and pork, juice, milk, and sugary drinks). Participants will be randomized to 1 of 4 between-subjects experimental arms representing different message topics: a control arm or 1 of 3 intervention arms: health, environment, or health + environment.

Participants will be in the same experimental arm for all 4 experiments. In each of the 4 experiments, participants will view 2 messages from their assigned arm in random order and rate each message. (There will be 3 possible health, environment, and health + environment messages for each of the 4 target dietary substitutions. Participants in these experimental arms will view 2 of these 3 messages, selected at random. There are only 2 possible control messages; participants in the control arm will view these 2 control messages. In all experimental arms, the 2 messages will be shown in random order). In total, participants will rate 8 messages: 2 messages for each of the 4 experiments.

## **Objective**

The objective of this study is to examine the effect of message topic on perceived message effectiveness for encouraging healthy and sustainable dietary substitutions. We will compare dietary substitution messages focused on health, the environment, both health + environment, or a control topic. We hypothesize that messages about health, the environment, or both health + environment will receive higher perceived message effectiveness ratings than messages about the control topics.

## **Statistical Considerations**

### **General Principles**

We will use a two-sided critical alpha of 0.05 to conduct all statistical tests. All confidence intervals presented will be 95% and two-sided. Analyses will include all randomized participants according to experimental conditions they were randomized to (i.e., intent-to-treat). Participants will be prompted to respond to all survey questions before they can continue, so we expect there will be minimal missing data and therefore plan to use complete case analysis.

### **Overview**

Participant characteristics will be descriptively summarized by experimental arm prior to analysis. Means and standard deviations will be used to characterize continuous variables, and frequencies and percentages will be used to describe categorical variables.

### **Primary Outcome**

The primary outcome is perceived message effectiveness (PME). We will assess PME with 4 items: 3 items adapted from Baig and 1 item adapted from Jongenelis. The items will be tailored to each of the 4 target dietary substitutions (beef/pork, juice, milk, and sugary drinks), as shown below:

1. *How much does this message discourage you from wanting to [eat beef and pork / drink juice / drink cow's milk / drink sugary drinks]?*
2. *How much does this message make [eating beef and pork / drinking juice / drinking cow's milk / drinking sugary drinks] seem unpleasant to you?*
3. *How much does this message make you concerned about the effects of [eating beef and pork / drinking juice / drinking cow's milk / drinking sugary drinks]?*
4. *How much does this message make you want to [eat chicken or vegetarian options instead of beef and pork, eat whole fruit instead of drinking juice / drink non-dairy milk instead of cow's milk / drink water instead of sugary drinks]?*

Responses options for each item are presented as a Likert-type scale: Not at all (coded as 1); Very little (2); Somewhat (3); Quite a bit (4); A great deal (5). We will average responses to these 4 items to create a PME score for each message, assuming sufficient internal consistency (Cronbach's alpha $\geq$ .70).

### **Statistical Analyses**

We will run separate analyses for each of the 4 experiments (i.e., for each of the 4 dietary substitutions). For each experiment, we will conduct the following analyses:

1. First, primary analyses will use mixed effects linear regression models to **examine whether the intervention *topics* receive higher PME ratings than the control *topic*.**

We will regress PME on indicator variables for the experimental arms (health, environment, or health + environment, treating the control as the referent group). The coefficients on the indicator variables for the intervention topics are average differential effects (ADEs) indicating the difference in mean PME between the intervention topic messages and the control topic messages. Our hypothesis will be supported if the coefficients on the indicator variables for the intervention topics are positive and statistically significant. For these planned primary analyses, we will not correct *p*-values for multiple comparisons.

2. Second, secondary analyses will use mixed effects linear regression models to **examine whether the intervention *topics* receive different PME ratings than one another.** We will use the same model as in (1) to compare the ADEs for each intervention topic to one another using Chi-Squared tests. These analyses will correct *p*-values for multiple comparisons using the Bonferroni-Holm procedure, considering 3 tests to compare each intervention topic to the others.
3. Third, we will **descriptively rank the messages.** We will estimate mean PME for each message statement and rank those means. These analyses will be descriptive (i.e., we do not plan to perform hypothesis tests).

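### Does testing message topics with only two or three messages each require a message-level term or a rule limiting the conclusions?

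*Combined protocol and SAP*

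**What the plan says.** The wording moves between topics and messages.

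- **Topic wording.** The Introduction says "This analysis examines the effect of different message topics", and the Objective section says "The objective of this study is to examine the effect of message topic on perceived message effectiveness". The synopsis, in its analytic plan for secondary outcomes, uses mixed models to "examine the effect of each intervention topic on perceived message effectiveness compared to the other intervention topics". Statistical Analyses, item 1, gives the support rule: "Our hypothesis will be supported if the coefficients on the indicator variables for the intervention topics are positive and statistically significant".
- **Message wording.** The primary and secondary objectives in the synopsis compare messages with messages. So does the hypothesis sentence in the Objective section. Item 1 of Statistical Analyses explains the coefficients as "indicating the difference in mean PME between the intervention topic messages and the control topic messages". Sample Size and Power also sets intervention messages against control messages.
- **Materials.** The Study Protocol section states: "There will be 3 possible health, environment, and health + environment messages for each of the 4 target dietary substitutions". Each participant in those arms sees two of the three, chosen at random. For control: "There are only 2 possible control messages; participants in the control arm will view these 2 control messages".
- **Model.** Item 1 says "We will regress PME on indicator variables for the experimental arms". The models are called mixed effects, but no random effect is named, so a message term is neither planned nor excluded. Item 3 adds a descriptive ranking of message means without tests.

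**The concern.** A result for three particular health messages differs from a result for health messaging as a whole. If the messages are regarded as a sample from many that could have been written on the topic, the choice of messages adds uncertainty to the topic contrast. A model with arm indicators and a participant intercept leaves that uncertainty out, and recruiting more participants does not reduce it.

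The objective and the support rule speak of topics, and nothing in the plan restricts the conclusion to the messages shown. A reader could therefore take a significant coefficient as proof about the topic, with a p-value that is too small for that claim. The secondary comparisons are exposed as well, because they set one topic against another.

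**Working it through.** **Inputs from the documents.** Sample Size and Power gives 400 participants per arm, two ratings per participant in each experiment, a correlation of 0.5 and target d = 0.20 versus control. Alpha is 0.05 two-sided, or 0.0167 for comparisons between intervention topics. The Study Protocol gives three messages per topic and two for control.

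**Input not in the documents.** The between-message SD within a topic, s, is assumed to be 0, 0.05 or 0.10 in units of the PME SD.

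**Step 1: the plan's own figure.**
- Variance of a participant's mean of two ratings: (1 + 0.5)/2 = 0.75.
- SE of the difference between two arms: sqrt(2 × 0.75/400) = 0.0612.
- Power at d = 0.20 and alpha 0.05: 0.904, which agrees with the stated 90%.

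This is power for the messages shown, because the formula contains no message variance.

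**Step 2: the contrast the plan defines.** For a difference between the tested messages of two arms, the messages are fixed and the SE of 0.0612 is the right one. The per-contrast error rate is 5% two-sided, or 2.5% in the positive direction, whatever s is.

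**Step 3: the wider claim.** For a claim about the topic in general, the variance gains:
- versus control, control messages a sample: s²(1/3 + 1/2)
- versus control, control messages fixed: s²/3
- between two intervention topics: s²(1/3 + 1/3)

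False positive support versus control is P(Z > 1.960 × 0.0612/SE). The two-sided rate between topics at the first Holm threshold is 2 × P(Z > 2.394 × 0.0612/SE).

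| Contrast | SE at s = 0 / 0.05 / 0.10 | False support |
|---|---|---|
| Versus control, control a sample | 0.0612 / 0.0764 / 0.1099 | 2.5% / 5.8% / 13.7% |
| Versus control, control fixed | 0.0612 / 0.0677 / 0.0842 | 2.5% / 3.8% / 7.7% |
| Between topics | 0.0612 / 0.0736 / 0.1021 | 1.7% / 4.6% / 15.1% |

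The rows versus control are per contrast. If the support rule is read as needing all three coefficients positive and significant, the rates are 0.2% / 0.7% / 3.3% with control a sample and 0.2% / 0.2% / 0.3% with control fixed.

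**Step 4: what a message random effect would bring.** Suppose a topic claim also had to be supported by a sensitivity model with a message intercept crossed with participant and Satterthwaite degrees of freedom (simulation, 4,000 experiments per setting, control messages a sample unless stated).
- False support versus control becomes 2.0% / 2.6% / 2.4%.
- Power at d = 0.20 falls to 88% / 69% / 39%.
- The message SD is poorly estimated from 11 messages (3 × 3 + 2). The central 90% of estimates runs from 0 to 0.09 for a true 0.05, and from 0.04 to 0.15 for a true 0.10.
- The model assumes equal message variance across arms. If control messages do not vary and topic messages have SD 0.10, the false-positive rate between topics is 3.2% against a nominal 1.67%.

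**The case for a change.** The strongest case for a change is that the gap is real and cheap to close. No sentence sets the scope of inference, the objective and the analysis question name topics, and the message ranking is not linked to the support rule. An SD of 0.10 means that only 1% of PME variance lies between messages, yet it is half the effect the study is powered for. A scope sentence and one extra model per experiment would leave the primary test untouched and would prevent the scope from being chosen after the results are known.

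The arithmetic of this case stands, and so does the absence of a scope sentence. The claimed mismatch is weaker than it looks. The support rule refers back to a hypothesis worded for messages, the synopsis objectives are worded the same way, and the Study Protocol section uses topics to label the arms. Read together, a topic in this plan is its set of messages. A scope sentence would state that reading without altering any estimate, interval or test.

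The extra model is a matter of judgement. It protects a general topic claim at a clear cost in power, and it relies on a variance and an equal-variance assumption that two or three messages per arm can hardly support. Reasonable statisticians would differ on whether to run it, and it would be a poor basis for a decision rule.

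**Conclusion.** No change to the plan is needed. The planned contrast is between the messages tested. For that contrast, with a participant intercept as the ordinary reading of the unnamed mixed model, the error rate is nominal and the 90% power versus control stands.

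Harm would arise only if a report carried the result beyond those messages. Its size cannot be derived from the documents: per contrast versus control, false positive support is 2.5% at an assumed message SD of 0, 3.8% to 5.8% at 0.05 and 7.7% to 13.7% at 0.10, depending on whether the control messages are fixed or a sample.

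What is missing is a detail of interpretation that analysts can supply by reporting the contrasts as results for the messages shown, next to the message means already planned in item 3. A crossed message random effect is an optional trade-off.

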## Sample Size and Power

We used G\*Power 4 to estimate sample size needs to detect an effect of the health, environment, or health + environment messages vs. the control messages using a repeated measures ANOVA examining between-subjects factors. We estimated power assuming an alpha=0.05, correlation among repeated measures of 0.5 (a conservative estimate based on prior studies), and 2 repeated measures (reflecting that participants will rate 2 messages for their

assigned topic in each of the 4 experiments). Under these assumptions, a sample size of 400 participants per experimental arm (1,600 participants total) will yield 90% power to detect a small standardized effect of Cohen's  $f=.10$  (or Cohen's  $d=.20$ ) or larger. To our knowledge, there are not similar studies of dietary substitution messages, so we powered to detect a small standardized effect size. The planned sample size will also yield 90% power to detect effects of Cohen's  $f=.11$  (or  $d=.22$ ) or larger for comparing each intervention topic vs. the other intervention topics, assuming an  $\alpha=0.0167$  (i.e., 0.05 divided by 3, to correct for multiple comparisons).

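### The fixed effects in the four primary models are the arm indicators only; adding randomised experiment position and age is an optional, nearly cost-free gain in precision

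*Combined protocol and SAP*

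**What the plan says.** Statistical Analyses gives each substitution its own model: "We will run separate analyses for each of the 4 experiments". Item 1 states that "primary analyses will use mixed effects linear regression models to" compare each intervention topic with control, and then "We will regress PME on indicator variables for the experimental arms", with control as the referent. No other fixed effect is listed. Item 2 uses the same model to compare the intervention topics with one another.

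Three other places bear on this:

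- **Study Protocol.** Arm is fixed for a participant across all four experiments, but "participants will complete 4 experiments in random order". Within an experiment, "In all experimental arms, the 2 messages will be shown in random order".
- **Overview.** "Participant characteristics will be descriptively summarized by experimental arm prior to analysis". The characteristics are not named, their timing is not given, and no use beyond description is stated.
- **Synopsis and Exclusions.** Age determines eligibility, and the synopsis places eligibility screening before the intervention phase.

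Sample Size and Power assumes 400 participants per arm, two ratings per experiment and a "correlation among repeated measures of 0.5". It uses no covariates.

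**The concern.** A participant meets each substitution once, at one position. In the model for, say, juice, position is therefore constant within a participant and varies between participants. Arm also varies only between participants. If ratings drift as the survey proceeds, through fatigue or familiarity, that drift adds to the variance against which the arm contrasts are tested. The same holds for age if it predicts PME.

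Message order within an experiment is different. Every participant rates one message first and one second, so order is balanced within each participant's mean and adds nothing comparable to the arm contrasts.

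Position is randomised, and age cannot be changed by the messages. In a linear model, adjusting for either leaves the target unchanged: it is still the difference in mean PME between arms. What is at stake is some precision in the twelve primary contrasts (three per model in four models) and in the secondary contrasts that reuse those models. A covariate list also has most value if fixed before data are seen, which is the status the Introduction claims for the plan.

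**Working it through.** **Inputs from the documents.** 400 per arm; m = 2 ratings; correlation ρ = 0.5; f = 0.10 (d = 0.20); two-sided alpha 0.05 (Sample Size and Power; General Principles). **Assumed:** R², the share of the variance of a participant's mean rating that the added terms explain. The documents give no value.

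**1. The plan's own figure.** For a between-subjects factor in a repeated-measures ANOVA, the noncentrality is λ = f²·N·m / [1 + (m − 1)ρ]. For one intervention arm against control, N = 800:

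λ = 0.01 × 800 × 2 / 1.5 = 10.67, which gives power of 90.4%.

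The stated 90% reproduces. A four-arm overall test with N = 1,600 would give 98.2%, so the plan's figure is the pairwise contrast. As a cross-check, the SD of a mean of two ratings is √(1.5/2) = 0.866, the standard error (SE) of a contrast is 0.866 × √(2/400) = 0.0612, and 90% power needs 395 per arm.

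**2. How much position could explain.** Positions 1 to 4 are equally likely, so their variance is (1.5² + 0.5² + 0.5² + 1.5²)/4 = 1.25. With a linear drift of s SD per step added to the planning variance of 0.75, the share is 1.25s² / (0.75 + 1.25s²):

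| Assumed drift per step | Share due to position |
|---|---|
| 0.05 SD | 0.4% |
| 0.10 SD | 1.6% |
| 0.20 SD | 6.3% |

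The last row implies 3 × 0.20 = 0.60 SD from first to fourth position, three times the effect the trial is powered to detect. It is an upper bound and not an expectation.

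**3. Primary power after adjustment.** λ is divided by (1 − R²) and the SE is multiplied by √(1 − R²):

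| Assumed R² | λ | SE (SD units) | Power at d = 0.20 |
|---|---|---|---|
| 0 | 10.67 | 0.0612 | 90.4% |
| 0.004 | 10.71 | 0.0611 | 90.5% |
| 0.02 | 10.88 | 0.0606 | 90.9% |
| 0.05 | 11.23 | 0.0597 | 91.7% |
| 0.10 | 11.85 | 0.0581 | 93.0% |

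**4. Cost if the terms are useless.** With 1,600 participants and four arm means, 3 pure-noise terms inflate the SE by √(1596/1593) = 1.0009 and 10 terms by √(1596/1586) = 1.0031, so by about 0.1% to 0.3%.

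**5. Cost if a covariate has gaps.** λ is proportional to N/(1 − R²), so losing a fraction L of participants cancels the gain when R² = L. With 1% lost (396 per arm, N = 792) and R² = 0.01, λ = 0.01 × 792 × 2 / 1.5 / 0.99 = 10.67, exactly where it began.

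**6. Secondary comparisons.** At f = 0.11 and alpha 0.0167, λ = 0.0121 × 1,600 / 1.5 = 12.91 and power is 88.3%. At f = 0.1127, λ = 13.55 and power is 90.0%; that f prints as 0.11.

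**The case against.** The strongest reply is that nothing here is wrong. Arms are randomised, the unadjusted contrasts are unbiased, and the arm-only model matches a power calculation made without covariates. That stands, and it fixes the weight of this point as optional.

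The size of the gain is also assumed throughout. No section gives an R-squared or a drift, or says that age predicts PME, and an age range of 18 to 25 may leave age little to explain. The documents do not say that the survey stores position, although a randomised order can be stored. That stands too, and is why the range starts near zero.

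A reader might infer more, in four ways that the documents do not support:

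- **That the secondary comparisons are underpowered and need rescue.** The 88.3% at f = 0.11 is largely rounding (step 6). Alpha 0.0167 is also only the strictest step of the Bonferroni-Holm procedure.
- **That adjustment is the only way to gain precision without enrolling more people.** The design itself shows another: each intervention topic has three messages per substitution and a participant rates two.
- **That adjustment can only help.** Useless terms cost a little (step 4), and under the complete-case rule in General Principles a covariate with gaps could cost more than it returns (step 5).
- **That a set of baseline characteristics is ready for use.** Overview names none and does not say whether they are asked before or after the messages.

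It would also be loose to say that the models contain nothing but arm. They are mixed models with a random part, whose structure is not given; the point concerns the fixed effects.

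**Conclusion.** The point holds as an optional gain in efficiency. The listed fixed effects are the arm indicators alone. Experiment position and age are between-participant factors within each model and could be added without changing what is estimated. If they, and any suitable demographics, remove 0.4% to 10% of the variance of a participant's mean rating, primary power at d = 0.20 moves from 90.4% to between 90.5% and 93.0%. That range rests on assumed variance shares, the plan's correlation of 0.5 and 400 analysed participants per arm. The true gain may be close to zero. The unadjusted analysis remains valid, unbiased and consistent with the stated power, and the study's conclusions do not depend on this change.

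**What to change.** Before data collection, add to Statistical Analyses, item 1, that each of the four models includes experiment position (1 to 4, categorical) and age as fixed effects beside the arm indicators. Confirm that the survey stores position. Add further demographics only if they are named in the plan, have complete data, and are either measured before message exposure or not alterable by the messages. Keep the arm-only model as a sensitivity analysis. Item 2 reuses the model and would follow without a separate change.

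The cost is a sentence and a short fixed list. The statistical price is an SE about 0.1% to 0.3% larger if the terms explain nothing. The main risk is losing participants to a missing covariate under the complete-case rule, which the completeness condition avoids.
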